COVER PAGE

Official title: Effect of general and regional anesthesia on endothelial glykokalyx

NTC number: NCT02783443

Date of the document: 7. 11. 2019

Objective: The aim of the observational study was to evaluate the changes of PBR in patients undergoing elective joint surgery under general (GA) vs. neuraxial anesthesia (NA). Our hypothesis was that PBR will be lower in patients in NA.

Hypothesis to be tested: Regional anaesthesia affects GCX less than general anaesthesia.

Design: Two center prospective observational study.

Methods: Sixty consecutive patients (ASA 1-3) undergoing elective total knee or hip replacement under GA or NA were included in this prospective observational cohort study. PBR in the sublingual microcirculation was recorded in each patient using SDF at two time points - before surgery and 2 hours after surgery.

Scientific background: Damage of the endothelial glycocalyx (EG) has been described during surgery, but the effect of different anesthesia techniques remains unknown. Perfused boundary region (PBR) evaluated by side-stream dark field (SDF) imaging of the sublingual microcirculation enables *in vivo* EG assessment. PBR values are inversely related to the EG thickness.

Statistical considerations: Based on the expected difference in PBR between patients under GA and NA, the alpha error  $\alpha = 0.05$  and study power = 0.99, sample size calculation was 52 patients. We aimed to enrol 60 consecutive patients to reach 30 patients with each type of anesthesia, either general anesthesia or neuraxial.

For statistical analysis, we used Graph Pad Prism v6.0c (GraphPad Software, Inc., CA, USA). All data were tested for normality prior testing by D'Agostino-Pearson omnibus normality test. Data are expressed as mean (and standard deviation) or median (and interquartile range), a value of  $p \leq 0.05$  was considered as statistically significant for paired and unpaired t-tests. Z-test we used for two populations proportion analysis.

Chief Investigator: [name]

Sponsor Number: AZVCR 15-3881/A, all rights reserved.

Name of site: Hradec Kralove

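### The hypothesis is causal, but the GA–NA comparison of PBR rests on an unadjusted t-test that cannot separate anaesthesia type from centre, joint or ASA class

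*Combined protocol and SAP*

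**What the plan says.** The Design line calls this a "Two center prospective observational study". Methods states that "Sixty consecutive patients (ASA 1-3) undergoing elective total knee or hip replacement under GA or NA were included in this prospective observational cohort study". The document does not say how anaesthesia type was chosen or how the two techniques were spread over the centres, and it names one site.

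The hypothesis appears in two forms. Under Hypothesis to be tested it is causal: "Regional anaesthesia affects GCX less than general anaesthesia". Under Objective it is descriptive: "Our hypothesis was that PBR will be lower in patients in NA".

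The compared outcome is left open. The Objective is to "evaluate the changes of PBR in patients undergoing elective joint surgery". PBR was "recorded in each patient using SDF at two time points - before surgery and 2 hours after surgery". The sample size is "Based on the expected difference in PBR between patients under GA and NA", without saying whether that difference is in the 2-hour value or in the change. With alpha 0.05 and power 0.99 the calculation gives 52 patients, and "We aimed to enrol 60 consecutive patients to reach 30 patients with each type of anesthesia".

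Statistical considerations names a normality test, paired and unpaired t-tests, and a z-test for two proportions. It names no covariate, matching, stratification or regression.

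**The concern.** When technique is not assigned, the two groups can differ in ways that themselves bear on PBR. The document identifies three such candidates: centre, joint (hip or knee) and ASA class. If any of them differs between GA and NA and is related to the compared outcome, the GA–NA difference is biased. No step in the plan removes that bias. Enrolling more patients does not help, because the bias equals the imbalance times the factor's effect whatever the sample size. The planned power of 0.99 protects only against a false negative.

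A positive unadjusted result could support the Objective's statement that PBR is lower under NA. It could not support the claim that the technique *affects* the glycocalyx less.

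**Working it through.** **1. Which test compares PBR between groups.** The paired t-test is within patient. The z-test is for proportions; if it was meant for joint or ASA class, it could reveal imbalance but not adjust PBR for it. That leaves the unpaired t-test. This is by elimination, since the text assigns no test to a comparison.

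**2. Which factors matter.** If change (2 hours minus pre-operative) is compared, a factor that adds the same amount to both readings cancels, and only factors that shift the perioperative change can bias the result. If 2-hour PBR is compared, factors that shift level or change can.

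**3. The plan's own figure.** The 52 cannot be reproduced, because no PBR difference, SD or sidedness is given. Solving backwards for 26 per group, two-sided:

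d = (1.960 + 2.326) × √(2/26) = 1.19 SD (normal approximation), or 1.212 with the t distribution. Power at 30 per group is then 0.996.

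**4. Size of the problem (assumed inputs, not from the document).** Take 30 per group, no true effect, and one binary factor with prevalence p in one group and 1 − p in the other. Then D = 2p − 1, and the factor's effect is b = 0.5 SD.

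δ = [bD / √(1 + b²p(1 − p))] × √(30/2); false-positive rate = Φ(δ − 1.96) + Φ(−δ − 1.96).

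At 70/30: δ = (0.2/1.026) × 3.873 = 0.755, so the rate is 0.114 + 0.003 = 11.7%. The formula gives 6.6%, 20.7% and 33.5% at 60/40, 80/20 and 90/10.

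Simulation agrees (20,000 runs per cell, pre–post correlation 0.5; joint and three-level ASA class also in the models and unrelated to group):

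| Analysis and factor | 60/40 | 70/30 | 80/20 | 90/10 |
|---|---|---|---|---|
| t-test on change, factor shifts level only | 4.9% | 4.7% | 4.9% | 5.0% |
| t-test on change, factor shifts change | 6.7% | 11.7% | 20.6% | 32.0% |
| t-test on 2-hour PBR, factor shifts level | 6.7% | 11.4% | 20.2% | 32.6% |
| Adjusted change model, factor shifts level only | 5.1% | 5.3% | 5.1% | 4.8% |
| Adjusted change model, factor shifts change | 5.2% | 5.0% | 5.2% | 4.8% |

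A bias of 0.171 SD is enough to double the error rate to 10%.

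**5. Precision cost of adjustment.** The SE is multiplied by 1/√(1 − D²):
- 70/30: 1/√0.84 = 1.09
- 80/20: 1/√0.64 = 1.25
- 90/10: 1/√0.36 = 1.67

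Residual df fall from 58 to 54 (one for centre, one for joint, two for ASA class), or to 53 with pre-operative PBR.

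| Power of adjusted change model | 70/30 | 80/20 | 90/10 |
|---|---|---|---|
| d = 1.212, analytic | 0.988 | 0.958 | 0.790 |
| d = 1.212, simulated | 0.980 | 0.930 | 0.721 |
| d = 0.8, analytic (unadjusted 0.861) | 0.796 | 0.682 | 0.447 |

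**6. What adjustment does not solve (same simulation).**
- An unmeasured 0.5 SD factor acting on the change leaves 11.5%, 19.6% and 31.1% false positives in the adjusted change model (70/30, 80/20, 90/10).
- An unmeasured 0.5 SD level factor gives about 5% in the change model, but 6.6%, 9.1% and 13.0% in the baseline-adjusted 2-hour model.
- If the groups differ in pre-operative PBR by 0.3 to 0.5 SD and that gap regresses, the change model gives 8.5% to 15.0% and the baseline-adjusted model about 5%.

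**The case against.** The harm is hypothetical: the document shows no imbalance, and no relation of these factors to PBR. If change is compared, which fits the Objective, and the factors shift level only, the unadjusted t-test is sound. This stands, and it limits the claim to what the plan cannot separate.

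The study calls itself observational and the Objective's hypothesis is descriptive, so rewording alone might be enough. Rewording does answer the causal claim. It does not remove a measurable imbalance from the estimate.

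The choice between a change model and a baseline-adjusted model is not settled by the document, and step 6 shows that each fails where the other holds. This is a fair point and the reason to report both. The change model comes first only because the Objective speaks of changes.

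The figures assume a correlation of 0.5, where the SD of change equals the SD of level. With effects expressed in SDs of level, unadjusted false positives for a shift in change at 90/10 would be 25% at correlation 0.3 and 50% at 0.7. Adjusted power at 90/10 would be 0.647 and 0.946. With effects expressed in SDs of the compared outcome, this dependence disappears. Either way the numbers are illustrative.

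Three covariates do not license a causal claim, and the document does not list the factors as recorded data. Both points are correct. The first is why the conclusion should be associational. On the second, the factors follow from design and eligibility, so they should be retrievable.

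**Conclusion.** The concern holds and should be fixed. Followed as written, the plan leaves any imbalance in centre, joint or ASA class in the GA–NA difference, while the hypothesis to be tested is causal. Bias is possible, not demonstrated. Its size depends on imbalances and factor effects that the document does not give, so the illustrative false-positive rate runs from about 5% (change compared, level-only factor) to about 32% (0.5 SD on the compared outcome, 90/10). Confidence is high that adjustment is missing; nothing here shows that the results are in fact biased. The power figures rest further on 52 being the total, a two-sided test and an undisclosed planning effect.

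**What to change.** - State the compared outcome. Make the between-group analysis a linear model of change in PBR on anaesthesia group, with centre, joint and ASA class as covariates, and report the adjusted difference with its 95% CI.
- As a sensitivity analysis, report 2-hour PBR adjusted for pre-operative PBR and the same covariates. Say that the two models rest on different assumptions when groups are not randomised.
- Keep the unpaired t-test as supportive, and tabulate the three factors by group.
- If technique coincides with centre, omit centre and state that the comparison cannot be separated from it.
- Word the conclusion as an association.
- The plan is written in the past tense, so label the model as not prespecified if it is added after the data were seen.

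The work is revised SAP wording, one table and two regressions, with no new patients. The statistical price is lost precision: small at 70/30 if the planning effect is near 1.21 SD, but substantial at 90/10 or if the true effect is nearer 0.8 SD.

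### Does enrolling 60 consecutive patients, with anaesthesia not assigned by the study, undermine the target of 30 per group and the 0.99 power?

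*Combined protocol and SAP*

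**What the plan says.** The Design entry calls this a two-centre prospective observational study. The Methods report that "Sixty consecutive patients (ASA 1-3) undergoing elective total knee or hip replacement under GA or NA were included". Under Statistical considerations the calculation, at a two-group alpha of 0.05, is given as "study power = 0.99, sample size calculation was 52 patients". The recruitment target comes next: "We aimed to enrol 60 consecutive patients to reach 30 patients with each type of anesthesia, either general anesthesia or neuraxial".

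The document gives no expected mix of general anaesthesia (GA) and neuraxial anaesthesia (NA) at the two centres, no quota or closing rule for a filled group, and no statement of what happens if the split is uneven. The sample size is described only as "Based on the expected difference in PBR between patients under GA and NA", without a numerical difference or SD. The analysis relies on t-tests, unpaired between the groups.

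**The concern.** Taken literally, the target sets two conditions that the study does not control together. The investigators do not choose the technique, so the composition of 60 consecutive patients depends on local practice. If one technique is commoner, either the groups end up unequal, or some patients having the commoner technique are passed over and the series is no longer strictly consecutive.

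Each outcome would carry a cost. Unequal groups give a less precise comparison than the calculation assumed. Passing patients over without a record would add a selection step to a study in which consecutive enrolment is the only stated protection against selective inclusion. A reader could reasonably ask whether the group sizes, and the 0.99 power built on them, can be relied on.

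**Working it through.** **Inputs.** From Statistical considerations: alpha 0.05, power 0.99, calculated size 52, planned enrolment 60 with 30 per group, unpaired t-test. Assumed, because the document is silent: 52 is a total (26 per group), the test is two-sided, SDs are equal, no PBR measurements are missing, and each patient independently has the same probability p of receiving the commoner technique.

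**Step 1: the plan's own figure.** The 52 cannot be reproduced forwards without a difference and an SD. It can be solved backwards for the standardised difference d.
- Normal approximation: d = (1.960 + 2.326) × √(2/26) = 1.19.
- Noncentral t, 50 degrees of freedom: d = 1.212.

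This is conditional on the plan's 52 and 0.99; it does not verify them.

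**Step 2: chance of the target split.** With X ~ Binomial(60, p):

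| Share p | P(30/30) | P(both groups ≥ 26) | P(both groups ≥ 19) |
|---|---|---|---|
| 50% | 0.103 | 0.755 | 0.997 |
| 60% | 0.030 | 0.341 | 0.928 |
| 70% | 0.0005 | 0.020 | 0.437 |
| 80% | about 0 | about 0 | 0.022 |

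An exact 30/30 is therefore unlikely without a per-group rule. But 26 per group is what a total of 52 requires; with 60 enrolled, the smaller group can be smaller than that.

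**Step 3: power at the split achieved.** The noncentrality is d × √(n₁n₂/(n₁+n₂)), with 58 degrees of freedom. For 30/30, n₁n₂/60 = 900/60 = 15, giving 1.212 × √15 = 4.70. For 19/41 it is 779/60 = 12.98, giving 4.37.

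| Split | Power at d = 1.212 |
|---|---|
| 30/30 | 0.996 |
| 26/34 | 0.996 |
| 20/40 | 0.992 |
| 19/41 | 0.990 |
| 18/42 | 0.988 |
| 15/45 | 0.979 |
| 12/48 | 0.959 |
| 11/49 | 0.947 |
| 10/50 | 0.931 |

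The 8 patients above 52 absorb imbalance down to 19/41, the last column of the Step 2 table. With a one-sided test (d about 1.12) the limit for 0.99 is again 19/41, with 0.980 at 15/45.

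**Step 4: power averaged over the random split.** Weighting the power at each split by its binomial probability gives 0.996 at p = 50%, 0.994 at 60%, 0.984 at 70% and 0.942 at 80%.

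**Step 5: a smaller effect.** At an illustrative d of 0.8, power is 0.86 at 30/30, 0.82 at 20/40 and 0.75 at 15/45. Of the gap between 0.99 and 0.82, 0.13 is already present with equal groups (0.99 − 0.86), and imbalance adds 0.04 (0.86 − 0.82). At 15/45 imbalance adds 0.11 (0.86 − 0.75).

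**Step 6: the two statements side by side.** The sentence on the target begins with an aim. Taking consecutive patients within each technique until 30 are reached is compatible with it. The Methods speak of 60 consecutive patients without saying whether that means overall or within technique. Nothing in the document describes skipping.

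**The case for a change.** The strongest case for acting is that consecutive enrolment is offered as the means of reaching 30 per group, and by itself it cannot ensure that. The document does not say which condition gives way, and a sentence plus a screening log would settle it. The 1.21 SD is back-solved and cannot be checked, so the margin in power could be an artefact of an optimistic effect size. If 52 meant patients per group, d would be about 0.85 and power would be 0.90 at 30/30, 0.86 at 20/40 and 0.67 at 10/50.

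Part of this stands. No mechanism for 30/30 is described, and a marked imbalance combined with a smaller effect would cost noticeable power. The per-group reading is less likely, since only 60 patients were planned in total. The unstated difference and SD are a separate and larger gap, which a recruitment rule would not close: even perfect balance leaves 0.86 at 0.8 SD. The selection concern depends on skipping that the document never mentions, and the within-technique reading avoids it except for a possible difference in calendar time between the groups. Finally, the document is dated 7 November 2019 and written in the past tense, so recruitment appears to be over and a new enrolment rule would have nothing to act on.

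**Conclusion.** No change to the plan is warranted. The observation about group sizes is correct: 30 per group is not secured by taking 60 consecutive patients, and exact balance has about a 10% chance even at a 50% share. Its consequence is small. Under the two-sided reading of 52 as a total, power holds at 0.99 down to 19/41, loses about one point at 15/45 (0.979), and falls below 0.95 only at 11/49 or worse. An uneven split costs precision; it does not in itself bias the unpaired t-test.

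What remains is an omitted detail that is sensibly filled when results are reported, by giving the achieved numbers per technique and saying whether patients were consecutive overall or within technique. Writing this into the plan would restate a target or drop it, with no gain for the comparison. The conclusion rests on the back-solved effect of about 1.21 SD, equal SDs, complete PBR data, and a local mix that is not extreme. At an 80% share, average power would still be about 0.94.

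### Does leaving the unpaired t-test unspecified (pooled or Welch), with 30:30 only an aim, put the 5% level of the GA–NA comparison at risk?

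*Combined protocol and SAP*

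**What the plan says.** The Statistical considerations section sets the significance rule in one sentence: p ≤ 0.05 "was considered as statistically significant for paired and unpaired t-tests". No variant of the unpaired test is named. The only assumption check described concerns shape: "All data were tested for normality prior testing", using the D'Agostino-Pearson test. Summaries may be means with SDs or medians with interquartile ranges.

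On group size, the same section says "We aimed to enrol 60 consecutive patients to reach 30 patients with each type of anesthesia". The Methods section describes consecutive patients who "were included in this prospective observational cohort study". No randomisation, quota or per-type stopping rule is mentioned. The sample size statement gives "study power = 0.99, sample size calculation was 52 patients", with no figure for the difference or the SD. The Methods section also says that "PBR in the sublingual microcirculation was recorded in each patient using SDF at two time points", before surgery and 2 hours after it.

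**The concern.** The GA–NA contrast is the study's hypothesis, and the unpaired t-test is the natural test for it. The pooled form assumes a common variance. If the smaller group is the more variable one, the pooled standard error is too small and the test rejects too often. If the larger group is the more variable one, the test is too strict and loses power. A normality test does not detect either case.

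Sixty consecutive patients whose technique is not assigned by the study need not fall 30:30. With no variant named and no SD given, a reader cannot exclude a p-value whose true level differs from 0.05. A PBR result summarised as a median would also sit beside a p-value for a difference in means.

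**Working it through.** **The plan's own figure.** The total of 52 cannot be rebuilt forwards, because neither the difference nor the SD is stated. Solving backwards, with two equal groups of 26 and a two-sided test (both assumed):

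d = (z₀.₉₇₅ + z₀.₉₉) × √(2/26) = (1.960 + 2.326) × 0.2774 = 1.19 SD

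The noncentral t gives 1.21 SD. At that effect, 30:30 has power of about 0.996.

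**Inputs.** From the document: α = 0.05, 60 patients, target 30:30. Assumed, because the document gives no values: normal data, other splits of 35:25, 40:20 and 45:15, and SD ratios up to 2.

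**Mechanism.** The true variance of the mean difference is σ₁²/n₁ + σ₂²/n₂. The pooled test estimates, on average,

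[((n₁−1)σ₁² + (n₂−1)σ₂²)/(n₁+n₂−2)] × (1/n₁ + 1/n₂)

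- At 30:30 with SDs 1 and 2: true 1/30 + 4/30 = 0.1667; pooled [(29 + 116)/58] × (2/30) = 2.5 × 0.0667 = 0.1667. They agree, as they must for any SDs when the groups are equal.
- At 40:20 with SD 1.5 in the smaller group: true 1/40 + 2.25/20 = 0.1375; pooled [(39 + 42.75)/58] × 0.075 = 0.1057. The standard error is too small by a factor of √(0.1057/0.1375) = 0.88.
- At 40:20 with SD 1.5 in the larger group: true 2.25/40 + 1/20 = 0.1063; pooled [(87.75 + 19)/58] × 0.075 = 0.1380. The standard error is too large by a factor of 1.14.

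**Type I error of the pooled test.** The rejection probability given the sample variances was averaged over 2,000,000 chi-square draws per setting. Paired entries are smaller group more variable / less variable.

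| Split | Equal SDs | SD ratio 1.5 | SD ratio 2 |
|---|---|---|---|
| 30:30 | 0.050 | 0.051 | 0.052 |
| 35:25 | 0.050 | 0.067 / 0.037 | 0.078 / 0.032 |
| 40:20 | 0.050 | 0.085 / 0.027 | 0.112 / 0.018 |
| 45:15 | 0.050 | 0.107 / 0.018 | 0.153 / 0.009 |

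Welch's test stays at 0.050 to 0.051 throughout.

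**How likely are the bad rows?** Suppose each of 60 patients independently has a 50% chance of GA (an assumption). The exact binomial then gives 35:25 or worse with probability 25%, and 40:20 or worse with probability 1.3%. Averaged over these splits, the pooled test's type I error is about 0.051 at SD ratios 1.25 and 1.5, and 0.054 at ratio 2. Gains and losses largely cancel, because either group may be the smaller one.

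**Power.** At 1.21 SD, the effect the plan's figures imply, Welch and pooled have power 0.996 and 0.996 at 30:30, and 0.990 and 0.991 at 40:20. The choice of variant hardly affects power.

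**The case for a change.** The strongest argument for acting is that the comparison is the main one, the variant is unnamed, and naming Welch costs almost nothing. If one technique is commoner, the averaging no longer cancels. At SD ratio 1.5 the pooled test's error averages 0.071 if the more variable technique has a 40% share, and 0.036 if it has 60%. These premises and figures stand as conditional statements. But the shares and SD ratios come from nowhere in the document, and the stated purpose of enrolling 60 was to obtain 30 of each type, which can be read as a per-type target. Harm needs the pooled form, an uneven split and unequal SDs together.

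A stronger remedy would be to regress post-surgery PBR on technique and pre-surgery PBR with robust (HC3) standard errors. That does not follow from the variance question. The objective concerns changes in PBR in a non-randomised cohort, where adjusted and change-score analyses can answer different questions. Take an assumed 0.5 SD baseline gap, a pre–post correlation of 0.5 and 30:30. If the mean change is the same in both groups, the adjusted model rejects about 17% of the time and a change-score t-test about 5%. If the outcome depends only on baseline, the change-score test rejects about 15% and the adjusted model about 5%. Neither is safer in general.

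Welch is no general cure either. For strongly skewed data (lognormal with sigma 1, 45:15, SD ratio 1.5, smaller group more variable), simulated error was 0.102 for Welch and 0.099 for pooled.

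The point about medians is speculative. The summary rule covers all variables, and nothing says PBR is the one shown as a median. The achieved split and SDs are results, which a plan does not contain.

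**Conclusion.** The omission is real but minor. At the design the plan describes, the choice between pooled and Welch is immaterial: type I error is at most 0.052 at 30:30 with one SD double the other, and 0.050 at any split with equal SDs. A clear departure, such as 0.085 or 0.027, needs a split near 40:20, an SD ratio near 1.5 and use of the pooled form. The document supports none of these. The wording already covers Welch's test, and an analyst facing visibly unequal groups and SDs would be expected to use it. Naming it would be a harmless clarification, but no conclusion of the plan depends on it. These figures assume normal data and 60 patients analysed.
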